4.2 SCIENTIFIC RATIONALE FOR STUDY DESIGN

The study design is a straight-forward clinical trial design with two arms. Participants will be randomized to each arm. There is no superior design than the one we have chosen. The control condition in this behavioral experiment is usual care, that is, the receipt of brochures containing radon information. As such, this is a straight-forward comparison of the new, or experimental approach, the use of a smartphone app, vs. usual care.

4.3 JUSTIFICATION FOR INTERVENTION

The mode of intervention delivery, the use of a smartphone, was defined in our previously published pilot study.¹¹ This was a college-aged population for which smartphone use is known to be highly prevalent (> 92% penetration into this demographic). Thus, this is a highly culturally and age-relevant intervention. The minimally acceptable participation rate was determined by our sample size calculations, presented in the published paper. These were exceeded.

4.4 END-OF-STUDY DEFINITION

A participant is considered to have completed the study if he/she has completed the baseline assessment and the 3-month follow-up assessment.

The end of the study is defined as completion of the 3-month follow-up assessment shown in the Schedule of Activities (SoA), **Section 1.3**.

5 STUDY POPULATION

5.1 INCLUSION CRITERIA

In order to be eligible to participate in this study, an individual must meet all of the following criteria:

1. Reading the informed consent form
2. Age \geq 18
3. Own a smartphone

5.2 EXCLUSION CRITERIA

An individual who meets any of the following criteria will be excluded from participation in this study:

1. Previous testing for radon within the past two years

5.3 LIFESTYLE CONSIDERATIONS

N/A

5.4 SCREEN FAILURES

Screen failures are defined as participants who consent to participate in this study but are not subsequently assigned to the study intervention or entered in the study. Individuals who do not meet the criteria for participation in this trial (screen failures) are automatically directed to the end of the pre-exposure survey.

5.5 STRATEGIES FOR RECRUITMENT AND RETENTION

COMM 110 and 102 students were invited to participate in the study. In the communication department, students enrolled in COMM 102 are required to complete the 2-hour research participation requirement. The participation in both pre- and post-exposure surveys in each experiment would allow them to meet an hour of participation requirement. For COMM 110, students receive extra .5% in their final grade per an half-hour research participation, and they are allowed to earn up to extra 2% (i.e., 2-hour research participation), according to COMM 110's extra credit policy. The participation in both pre- and post-exposure surveys in each experiment would allow them to earn extra 1% for their final grade (i.e., one-hour research participation).

Approximately 200 students are enrolled in COMM 102 each semester, and about 600 students are enrolled in COMM 110 each semester. They are included in the Communication Department's SONA website, which is the research participation pool website run by the department. Once the study is available on SONA website, students receive an email from SONA, and if they agree to participate in the study, they will sign up for the study on SONA website. They will be able to sign up for a 30-minute time slot for the pre-exposure survey session. Those who complete the pre-exposure survey will receive the same recruitment email encouraging them to sign up for another 30-minute time slot for their post-exposure survey session. This method was deemed appropriate to reach this target study population because they were familiar with the SONA system overall and receiving study notification emails.

Participants who agree to be in the study will receive a pre-exposure online survey link. Once they click on the link, they will be asked to read the consent form first. Screening questions will appear on the next page. Those who met the eligibility criteria were then able to proceed with the questionnaire and randomized. Those who did not meet the eligibility criteria were directed to the end of the survey.

Half of the participants assigned to the radon app condition will be asked to provide their Twitter information. If participants don't have a Twitter ID, they will be asked to create a new one prior to

completing the pre-exposure survey. Once the app is installed in participants' own phones and they successfully log in through their Twitter credentials, they will be asked to keep the app on their phone for three months with the notification setting "on". After all these steps are completed, they will be asked to complete the pre-exposure survey. The radon app can be accessed via computer or smartphone: <https://radon-production.herokuapp.com/>

The other half of the participants assigned to the brochure condition will be asked to provide the mailing address prior to completing the pre-exposure survey so that they can receive EPA brochures in the next 3 months via postal mail. Once this step is completed, they will be asked to complete the pre-exposure survey. During the 3-month period, participants assigned to the radon app condition will receive the radon educational materials via the app. Materials include the informational content repurposed from EPA brochures and radon-education Tweets using hashtags, such as #radon, #lungcancer, #healthylungs, and #radonawareness. The app uses the Twitter's mechanism so that's why participants need to use their Twitter credentials to login, and those hashtags used in Tweets are automatically detected by the app, and will be populated in the app. While keeping the app for three months, if participants would like to test their homes for radon levels, as education materials they will be exposed to encourage to do so, they can request a free radon kit through the app. They will be asked to enter their mailing address, email, and phone number so that the kit will be delivered to their home address. Although the app would collect such personal information, this is only to provide them with the free radon kit, and such information won't be attached to their any survey responses. On the other hand, participants assigned to the brochure condition will receive a total of three EPA brochures, with each one being delivered once a month. In each mailing, participants will receive a pre-addressed, pre-paid postcard to request a free radon test kit. The postcard will be addressed to a UND address so that we can track the number requested by participants in the brochure condition.

Participants who completed the pre-exposure survey then received an email reminder including the link for the post-exposure survey three months after the completion of their pre-exposure survey. Participants who did not complete the post-exposure survey two weeks after the initial email received a reminder email.

A sample size of at least 100 students in each group was determined to have a power of .8 to .9 to detect differences in proportions of at least 20%, Chi-square values of five or more with one or two degrees of freedom, mean differences of at least 0.3, and odds ratios greater than three in logistic regression.

Participant incentives:

Students who were enrolled in COMM 110 class received 0.5 extra course credit point for the completion of pre-exposure survey, which was equivalent to the half-hour research participation. If they completed the second and final session (i.e., post-exposure survey), they received additional 0.5 extra credit point.

Students who were enrolled in COMM 102 class met the half-hour research participation requirement for completing the pre-exposure survey. If they completed the second and final session (i.e., post-exposure survey), they met additional half-hour research participation requirement.

In addition to extra credit or meeting the research requirement, students received a \$10 gift card for the completion of pre-exposure survey. If they complete the second and final session (i.e., post-exposure survey), they received another \$15 gift card.

All students included in the Comm department's SONA research pool are 110 and 102 students, and they are taught by GTAs (110) and a designated instructor (102). The PI has never taught 102 or 110 courses, and will not do so. But in case any of PI's students are invited to the study, they will be given an option to complete an alternative task as a way to avoid coercion or undue influence.

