Description of Study Intervention/Experimental Manipulation:	
An online experiment with two experimental conditions using a pretest-posttest design: the radon app condition vs. brochure condition. Participants in both experimental conditions will complete an online pre-exposure survey during the baseline phase of the study. Upon completion of the pre-exposure survey, participants assigned to the radon app condition will be asked to install the radon app on their smartphones and use the app for three months. App installation will be verified electronically via text message sent to the investigators. To make the informational content of the radon app and EPA brochures equivalent, the informational content in the app condition will be repurposed from EPA brochures used in the brochure condition. Participants in the radon app condition will have the opportunity to order a free radon test kit through the app at any time during the three-month period.
 
In contrast, individuals assigned to the brochure condition will receive three EPA brochures for the three-month period via postal mails. These brochures are (1) Basic radon facts (https://bit.ly/2S6ryFw); (2) A citizen's guide to radon (https://bit.ly/3l3FhcJ); and (3) Consumer's guide to radon reduction (https://bit.ly/3ibt83n). In each mailing, participants will receive a pre-addressed, pre-paid postcard to request a free radon test kit. The postcard will be addressed to a UND address so that we can track the number requested by participants in the brochure condition.

Study Duration* :	6 months.
Participant Duration:	3 months.

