2.2 BACKGROUND

In collaboration with a media services company (Triad Interactive Media, Greensboro, NC), we developed a radon app for smartphones.¹¹ Briefly, the app uses a framework in HTML5 and the open source Twitter API. Posts created by the app are cross-listed on Twitter. Once users log in via Twitter, they can view radon news and mobile-friendly informative content on radon repurposed from EPA brochures. Users also can access existing Tweets containing hashtags, e.g., #radon, #radonawareness, #radonmitigation, and #lungcancer. Individual users' activities on the radon app, along with their Twitter handle, are saved on Triad Interactive Media's server. Through the app, users could order a free radon test kit at any time.

We conducted a pilot clinical trial using this app. Ninety six (96) undergraduates at the University of North Dakota in Grand Forks, ND (UND) were assigned to use the radon app for one month and were tested on several aspects of radon knowledge and testing using a pretest-posttest design.¹¹ We have recently published our findings.¹¹ We found that the use of the radon app: (1) significantly improved individuals' radon knowledge and generated positive attitudes toward radon testing; (2) significantly increased self-efficacy (i.e., an individual's perceived capability to order a radon test kit and use it); (3) significantly increased response efficacy (i.e., an individual's evaluation of the effectiveness of radon testing in preventing radon exposure); and (4) resulted in 24% of study participants ordering a free radon test kit. However, only a small percentage of participants actually used the test kit they obtained (i.e., employed the test in their home and returned it to the lab; a total test completion rate of 9%).

In summary, our pilot trial demonstrated that the radon app improved radon knowledge, motivation to test, and stimulated requests for free test kits. However, our pilot trial had a key limitation: there was no control group (i.e., a group not exposed to the app). Our present research builds and improves upon these preliminary findings. To do so, we will include a control group that receives usual care (radon information communicated via EPA brochures).

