4 STUDY DESIGN

4.1 OVERALL DESIGN

The project begins by comparing the role of the radon app vs. brochures on the percentage of participants that request free test kits and use and return them to the laboratory for analysis and improving knowledge about radon (Phase II).

Experimental design. We designed an online experiment with two experimental conditions—the radon app condition vs. brochure condition—using a pretest-posttest design. Study participants are undergraduates in the Communication Department at UND, indicating that this is a single-site trial. The principal eligibility criterion is that participants own a smartphone. The principal exclusion criterion is previous testing for radon within the past two years.

We consider UND undergraduates to be an appropriate population to test the app for several reasons: (1) ND has the highest residential radon levels in the U.S.²; (2) Our recent review of radon knowledge indicated that most individuals less than 30 years old do not know what radon is¹²; and (3) The age of many undergraduate students is similar to that of first time home-buyers in the U.S.¹³ We will assign recruited participants randomly to one of the two experimental conditions: app use and brochures.

Participants in both experimental conditions will complete an online pre-exposure survey during the baseline phase of the study. Upon completion of the pre-exposure survey, participants assigned to **the radon app condition** will be asked to install the radon app on their smartphones and use the app for three months. App installation will be verified electronically via text message sent to the investigators. To make the informational content of the radon app and EPA brochures equivalent, the informational content in the app condition will be repurposed from EPA brochures used in the brochure condition. Participants in the radon app condition will have the opportunity to order a free radon test kit through the app at any time during the three-month period.

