8 STUDY ASSESSMENTS AND PROCEDURES

8.1 ENDPOINT AND OTHER NON-SAFETY ASSESSMENTS

Once a participant will be directed to the Qualtrics pre-exposure survey link, the consent form will appear on the first page of the survey. Participants will be asked to read it and proceed if they agree. All participants will be asked to answer pre-exposure survey questions measuring key variables, such as radon knowledge, and demographic information to be used in the analyses (e.g., age, gender, home-owner status, smoking status). They will then be randomly assigned to one of the two conditions (via Qualtrics survey's randomization function). Participants assigned to the radon app condition will receive instructions on how to install the app and be instructed to use the app for the next three months. On the other hand, participants assigned to the brochure condition will receive appropriate instructions and be asked to submit both their mailing and email addresses so that they can receive three brochures in the next three months and be contacted for the post-exposure survey. Next, Participants' email and mailing addresses will not be attached to their responses to the pre-exposure survey to protect participants' privacy and confidentiality. Once participants complete the pre-survey, we have the data telling us that: which email address was assigned to which condition, and the timing. After 3 months, we will send the post-exposure survey link to that email address individually. Participants' behaviors,

which are two primary endpoints (i.e., test kit ordering and utilizing behaviors) will be recorded as they become available during the 3-month period.

In summary, participants in both experimental conditions will complete an online pre-exposure survey during the baseline phase of the study and then are randomized to the app or the brochure group. The experimental groups differ only in the means by which information is conveyed, not in the nature of the information. Participants in both conditions will have the opportunity to order a free radon test kit at any time during the three-month period.

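### Section 5.5 puts app installation and log-in before the pre-exposure survey, against sections 1.1, 4.1, 6.1.1 and 8.1; the two orders need reconciling to protect baseline knowledge (T1)

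*Combined protocol and SAP*

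**What the plan says.** The combined protocol and SAP describes the baseline session in several places.

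- **Section 5.5, app arm.** Twitter credentials, installation and log-in come first, and then "After all these steps are completed, they will be asked to complete the pre-exposure survey".
- **Section 5.5, brochure arm.** The structure is the same with a shorter step: participants "will be asked to provide the mailing address prior to completing the pre-exposure survey".
- **Section 5.5, earlier paragraph.** The questionnaire is named before randomisation: "Those who met the eligibility criteria were then able to proceed with the questionnaire and randomized".
- **Section 1.1.** "Upon completion of the pre-exposure survey, participants assigned to the radon app condition will be asked to install the radon app on their smartphones". Sections 4.1 and 6.1.1 use the same opening, "Upon completion of the pre-exposure survey, participants assigned to" the app condition.
- **Section 8.1, body.** All participants answer the pre-exposure questions, radon knowledge among them. They are then randomised in Qualtrics, and those assigned to the app then get installation instructions.
- **Section 8.1, summary.** Participants "will complete an online pre-exposure survey during the baseline phase of the study and then are randomized to the app or the brochure group".
- **Section 6.3.** Only people assigned to the app condition can download it.
- **Section 2.2.** "Once users log in via Twitter, they can view radon news and mobile-friendly informative content on radon repurposed from EPA brochures".

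Section 9.4.3 builds a 20-item knowledge index at T1 (baseline) and another at T2 (three months). The endpoint and the alternative hypothesis are worded as change. The test is a directional independent t-test of the difference in knowledge between groups, and the section does not say whether change scores or T2 scores enter it.

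**The concern.** A baseline measure is useful only if it is taken before either arm can be affected by its intervention. Under the order in 5.5, app participants would have a working, logged-in app before being asked to complete the survey that contains the T1 items. Brochure participants would have given a postal address and received nothing. Any early look at content would therefore raise T1 in one arm only.

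What is at stake is the secondary endpoint. Knowledge gained before T1 is subtracted from the app arm's change and not from the brochure arm's, so a real advantage of the app would be understated. Whoever programs the survey or interprets T1 needs one order, and the document gives two.

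**Working it through.** **1. The orders side by side.**

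| Place | Order given |
|---|---|
| 5.5, app paragraph | Twitter ID, installation, log-in, then survey |
| 5.5, brochure paragraph | Mailing address, then survey |
| 5.5, earlier paragraph | Screening, questionnaire, randomisation |
| 1.1, 4.1, 6.1.1 | Survey completed, then installation |
| 8.1 body | Knowledge questions, randomisation, installation instructions or address entry |
| 8.1 summary | Survey completed, then randomisation |
| 1.3 schedule | Baseline measures, knowledge, randomisation and intervention all on Day 1, with no order |

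Section 6.3 limits downloading to those assigned to the app. The 5.5 order therefore also requires randomisation before the survey is completed, which contradicts the 8.1 summary as well. The schedule of activities does not settle the matter.

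**2. Can one reading fit everything?** The nearest is: knowledge questions answered, then randomisation, then the arm-specific step, then the survey finished. It gives a clean T1. It fits the 8.1 body, the earlier paragraph of 5.5, and the 8.1 sentence "Once participants complete the pre-survey, we have the data telling us that: which email address was assigned to which condition". It does not fit 1.1, 4.1, 6.1.1 or the 8.1 summary, all of which have the survey complete before installation or randomisation. Nor do the app and brochure paragraphs of 5.5 say that part of the survey has already been answered. The text has to change somewhere.

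**3. Direction of any bias.** Suppose a share p of the app arm views content before T1 and gains g items on average. Assume that T2 knowledge is the same whether content was first seen just before or just after T1. Let m be mean true baseline knowledge in both arms, and A and B the mean gains to T2 in the app and brochure arms.

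- Observed T1: app m + p×g; brochure m.
- T2: app m + A; brochure m + B.
- Change-score contrast: (A − p×g) − B = (A − B) − p×g.
- T2-only contrast: (m + A) − (m + B) = A − B, so no shift.
- With T1 as a covariate and T1–T2 slope b: a shift of about −b×p×g.

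The documents give neither p nor g. Purely as an illustration, 30% gaining 1 item (0.30 × 1) or 10% gaining 3 items (0.10 × 3) each give p×g = 0.30. The shift is then −0.30 items on change, −0.15 with T1 as covariate at an assumed b of 0.5 (0.5 × 0.30), and 0 on T2. If T1 precedes log-in, p = 0 and every shift is 0.

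**4. Precision given up by T2 alone.** Relative to the T2 variance, adjustment for a clean T1 leaves 1 − r², and a change score has 2(1 − r), where r is the T1–T2 correlation. The documents do not give r, so a range is shown.

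| Assumed r | 1 − r² | T2-only sample multiple, 1/(1 − r²) | 2(1 − r) |
|---|---|---|---|
| .3 | .91 | 1.10 | 1.4 |
| .5 | .75 | 1.33 | 1.0 |
| .7 | .51 | 1.96 | 0.6 |

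Against a change score, T2 alone loses nothing up to r = .5. At r = .7 it needs 1/0.6 = 1.67 times the sample.

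**The case against.** The strongest reply is that the assessment section already gives the right order. The 8.1 body has knowledge questions, then assignment, then installation instructions, and 6.3 blocks the download before assignment. This stands. A reader of 5.5 alone might infer that the protocol nowhere places T1 before app content; 8.1 does, so the point is a conflict between sections and not an omission.

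A reader might also infer that T1 was in fact contaminated. The documents do not support that. The 5.5 order creates access, not shown exposure: nothing directs participants to read content during set-up, the session is a 30-minute slot, and 5.5 itself says the app arm receives its educational materials over the three-month period. Bias needs the 5.5 order to have been used, participants to have read content during set-up, and T1 to enter the test.

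It is tempting to turn this into a loss of power. That would rest on an invented amount of early learning and would vary with the T1–T2 correlation, which is not given. The 0.30 items used above happens to match the plan's mean difference of 0.3, which has no stated unit; the match follows from the chosen inputs and is not evidence.

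Finally, a reader might infer unequal loss of T2 data, because 5.5 sends the follow-up link to those who completed the first survey and the app set-up is longer. The documents give no completion figures by arm, and that is a separate question from the order of T1.

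None of this removes the contradiction, since no passage says which order governs.

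**Conclusion.** The inconsistency is certain: 5.5 cannot be followed together with 1.1, 4.1, 6.1.1 and the 8.1 summary. Its effect is conditional. If the 8.1 order was used, the effect is zero. If the 5.5 order was used and change is tested, the contrast shifts against the app by p×g items, an amount the documents do not allow anyone to estimate. With T2 scores alone there is no such shift, on the assumption that the timing of the first look does not alter T2 knowledge. The two primary endpoints, kits requested and kits returned, do not use T1. The point is minor and confined to the secondary endpoint.

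**What to change.** Rewrite the participant flow in 5.5 to the 8.1 order: consent, screening, all 20 knowledge items submitted, randomisation, then app installation and log-in or mailing-address entry. A closing survey page may follow the arm-specific step, so that course credit and the gift card stay tied to finishing the session. If such a page is kept, adjust the wording in 1.1, 4.1, 6.1.1 and the 8.1 summary to say that it is the knowledge items that are complete before randomisation and installation.

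If enrolment is already complete, as the past tense in parts of 1.1 and 5.5 suggests, state which order was used and report by arm the numbers randomised and the numbers completing baseline. If installation preceded the knowledge items, compare T2 knowledge between arms without using the app arm's T1 score.

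The cost is about one paragraph of text. Survey blocks need reordering only if they were built in the 5.5 order and enrolment is still open. The downside arises only in the T2-only case, which gives up the precision of a clean baseline, as tabulated above.

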10.1.1.2 CONSENT PROCEDURES AND DOCUMENTATION

The consent form for pre-exposure survey and post-exposure surveys will appear at the very beginning of each online survey. COMM110 and 102 students who are interested in participating in this study will be asked to read the consent form by themselves. Completion and return of the online survey form implies that they have read the information in this form and consent to participate in the research. Since the research presents no more than minimal risk and includes no procedures for which written consent is normally required outside the research context, the IRB granted the waiver of signature requirement for informed consent.

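### Section 5.5 puts Twitter and app setup after assignment but before the baseline survey, so app-arm loss can differ from brochure-arm loss, and no rule says how those who stop are counted

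*Combined protocol and SAP*

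**What the plan says.** **The order in 5.5.** After the consent page and screening, "Those who met the eligibility criteria were then able to proceed with the questionnaire and randomized". For the app arm, "If participants don't have a Twitter ID, they will be asked to create a new one prior to" the survey. The next steps are installation and login: "Once the app is installed in participants' own phones and they successfully log in through their Twitter credentials", they are to keep the app for three months, and then "After all these steps are completed, they will be asked to complete the pre-exposure survey". Brochure participants "will be asked to provide the mailing address prior to completing the pre-exposure survey", and nothing more is asked of them at that stage.

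**Other sections.** The synopsis and Sections 4.1 and 6.1.1 have app participants install once the pre-exposure survey is done. Section 8.1 has everyone answer the baseline questions, then be assigned, then receive instructions for their arm.

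**What survey completion controls.** Section 5.5 continues: "Participants who completed the pre-exposure survey then received an email reminder including the link for the post-exposure survey". Section 10.1.1.2 ties consent to it: "Completion and return of the online survey form implies that they have read the information in this form and consent to participate in the research". Sections 8.1 and 10.1.1.1 instead treat moving past the consent page as consent.

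**Who is counted.** Section 9.3 includes all randomised participants. Section 5.4 has this definition, cut here before its last two words: "Screen failures are defined as participants who consent to participate in this study but are not subsequently assigned to the study intervention or entered in". Section 7.2 bars replacement only for people who were randomised, received the intervention and then left.

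**The concern.** Tasks that follow assignment and differ by arm can undo randomisation. Opening a social-media account, installing an app and logging in is a much heavier request than typing an address. Sections 5.1 and 5.2 do not screen for willingness to use Twitter, so some app assignees may stop at setup, while comparable students in the brochure arm carry on.

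Under the 5.5 order, a student who stops there has no baseline knowledge score and is not sent the three-month link. The secondary endpoint needs both scores (9.4.3), so these students drop out of it, possibly in unequal numbers and for reasons related to motivation.

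For kit orders and returns the question is whether these students stay in the denominator. Section 9.3 says yes in general terms. Sections 10.1.1.2, 5.4 and 7.2 leave room to treat them as not consented, not entered or replaceable. If they were left out, the remaining app arm could be more motivated than the brochure arm, and the planned test is one-sided in the app's favour.

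**Working it through.** **Step 1: set the sequences side by side.**

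| Source | Sequence for the app arm | Can setup block the survey? |
|---|---|---|
| 5.5 | assignment, Twitter ID, install, login, survey | Yes |
| Synopsis, 4.1, 6.1.1 | survey, then install | No |
| 8.1 | baseline questions, assignment, install instructions | No app-only block described |

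The risk therefore exists only if the trial runs as 5.5 describes, and the plan does not say which sequence governs.

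**Step 2: trace a student who stops at setup under 5.5.**

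- Knowledge: no baseline score and no three-month link, so no change score. Section 9.3 gives no rule for such missing values. The documents give neither a loss rate nor a standard deviation, so no size can be put on this.
- Kits: orders arrive through the app or by postcard, and returns go to the laboratory. Both are recorded outside the surveys, so the student can still be counted, as a non-orderer, if kept in the denominator.

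**Step 3: illustrate the kit-order endpoint under both ways of counting.** The plan states no loss figure to reproduce.

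Inputs from the plan:
- 100 per arm (9.2).
- Directional Z test (9.2, 9.4.2).
- 24% order rate, from the uncontrolled app pilot (2.2).

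Assumed inputs:
- 24% is the true rate in both arms, so there is no effect.
- One-sided 5% level, since the plan states none.
- A share *d* of app assignees stops, and none in the brochure arm.
- Those who stop would have ordered at rate *q* = 10%.

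Formulas:
- App rate if stoppers are dropped: (0.24 − *d·q*) / (1 − *d*).
- App rate if stoppers are kept as non-orderers: 0.24 − *d·q*.
- Probability of rejection: Φ[(pA − pB − 1.645·SE0) / SE1], where SE0 uses the pooled variance and SE1 the unpooled variance.

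Example with *d* = 0.20, stoppers dropped, 100 followed per arm:
- App rate = (0.24 − 0.02) / 0.80 = 0.275.
- SE0 = √(2 × 0.2575 × 0.7425 / 100) = 0.0618.
- SE1 = √((0.275 × 0.725 + 0.24 × 0.76) / 100) = 0.0618.
- Φ[(0.035 − 0.1017) / 0.0618] = Φ(−1.08) = 0.14.

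| Stopping *d* | Dropped: app rate | Shift, points | False positives, 100 followed per arm | False positives, 100 assigned per arm | Kept: app rate | Rejection if kept |
|---|---|---|---|---|---|---|
| 10% | 25.6% | +1.6 | 8.2% | 8.1% | 23% | 3.5% |
| 20% | 27.5% | +3.5 | 14.0% | 13.5% | 22% | 2.4% |
| 30% | 30.0% | +6.0 | 24.5% | 22.2% | 21% | 1.6% |
| 40% | 33.3% | +9.3 | 42.6% | 36.0% | 20% | 1.0% |

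Sensitivity to *q*, stoppers dropped: with *q* = 15%, the shift for 20% to 40% stopping is 2.3 to 6.0 points. With *q* = 24%, it is zero and the test keeps its 5% level.

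**The case against.** A reader might infer that 5.5 establishes a run-in confined to the app arm, that anyone who stops is not consented, and that both primary endpoints are therefore biased towards the app. The documents do not support that much.

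- **The order is not settled.** The synopsis, 4.1 and 6.1.1 place installation after the survey. Section 8.1 makes nothing conditional on installation; the contact details it describes collecting after assignment are those of the brochure arm.
- **The brochure arm also has a step before the survey.** The burden is unequal rather than one-sided, and a new Twitter ID is needed only by those without one.
- **Consent is not clearly withheld.** Sections 8.1 and 10.1.1.1 take proceeding past the consent page as consent, and the screen-failure definition in 5.4 places consent before assignment. No section says that an assigned non-completer has not consented.
- **Section 9.3 already names all randomised participants.** With them kept, the illustrated app arm falls to between 20% and 23% against 24%. Failure to install is then part of the effect of the assigned strategy, and it works against the app.
- **The loss may be small.** Section 5.5 offers course credit and a $10 card for completing this survey.

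All of this stands, and it limits the claim about the kit endpoints. It does not remove the conflict over order, the missing rule for assigned students who never finish the survey, or the threat to the knowledge endpoint, which keeping full kit denominators cannot repair.

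**Conclusion.** The point holds in conditional form. The sections contradict each other on when app setup happens. If 5.5 is followed, loss after assignment can differ by arm. The direct consequence is for the knowledge comparison, where students who stop at setup have neither score; its size and direction cannot be derived from the documents.

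Inflation of kit orders or returns in the app arm needs two further conditions: stoppers are left out or replaced, and they are less likely to order than the rest. Under the assumed inputs, 10% to 40% stopping then adds about 1.6 to 9.3 points, with a false-positive rate of about 8% to 43% (about 8% to 36% if 100 are assigned rather than followed). If either condition fails, there is no inflation. The stopping shares and the stoppers' order rate are assumptions, and only kit orders were illustrated at these inputs, not returns.

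**What to change.** 1. Reconcile 5.5 with the synopsis, 4.1, 6.1.1 and 8.1. Everyone should complete consent, the full baseline survey, and email and mailing address before the Qualtrics randomiser fires. Twitter and app setup follow assignment.
2. Align 10.1.1.2 with 8.1 and 10.1.1.1, so that consent is recorded before assignment and does not depend on finishing a task specific to one arm.
3. State in 9.3 that everyone the randomiser assigns stays in the kit denominators and on the three-month contact list, whether or not the app is installed.
4. Amend 5.4 so that nobody already assigned can be a screen failure, and 7.2 so that nobody already assigned can be replaced.
5. Report by arm the numbers assigned, completing setup, completing the baseline survey and completing the three-month survey.

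The cost is reordering survey blocks and a few sentences of text. Assignees who never install will count against the app, which is the proper result for a comparison of assigned strategies. Asking about willingness to use Twitter before assignment is optional: it would reduce non-installation but narrow the population. If students have already been enrolled in the 5.5 order, items 3 and 5 still apply as far as Qualtrics records of assignment allow.
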